## 9. Section 4.1, Overall Design

**Description of change:** Clarified that an on-treatment biopsy is only required for participants in the biopsy subset.

**Rationale for change:** Investigator feedback.

## 10. Section 4.3, Study Termination

**Description of change:** Added text to reflect the responsibility of the head of study site (Japan) in regard to study termination.

**Rationale for change:** Requirement for Japan.

## 11. Section 5.1, Inclusion Criteria (Criteria 1 and 9)

**Description of change:** Added text to indicate the need for parental or legal guardian's consent for legally minor participants from Japan (Inclusion Criterion 1) and willingness to avoid pregnancy or fathering children for Japanese participants (Inclusion Criterion 9).

**Rationale for change:** Recommended standard practices in Japan.

## 12. Section 5.2, Exclusion Criteria (Criterion 11)

**Description of change:** Refined the wording regarding gastrointestinal abnormality.

**Rationale for change:** To further clarify and refine this exclusion criterion.

## 13. Section 6.1, Study Treatment Administered (Table 11: Study Treatment Information); Section 6.2, Preparation, Handling, and Accountability; Section 6.5.2, Management of Hyperphosphatemia

**Description of change:** Study treatment information for phosphate binders was added for Japan. Text was added to clarify that phosphate binders are provided by the sponsor and that the required documentation for binders is the same as for study drug in Japan. Text was also added to include the role of the investigational drug storage manager in Japan.

**Rationale for change:** Requirement for Japan.

## 14. Section 6.5.1, Criteria and Procedures for Dose Interruptions and Adjustments of Study Drug

**Description of change:** Added text regarding retinal detachment as well as guidance on the grading of retinal adverse events and clarified that re-escalation is not allowed after a dose reduction.

**Rationale for change:** To provide guidance on how to manage and grade SRD/RPED and investigator feedback.

[REDACTED]

[REDACTED]

[REDACTED]

[REDACTED]

## 16. Section 8.1.2, Prescreening and Screening Procedures

**Description of change:** A prescreening consent was added to the study. Participants will be required to sign a specific prescreening consent form if the site needs to consult with Incyte on the eligibility of a participant's genomic alteration. This is not required for all participants; it applies only to those whose genomic alterations need to be reviewed for eligibility.

**Rationale for change:** The Protocol was designed to guide the sites and provide as much information as possible on which genomic alterations are eligible for the study. As this field is evolving and new alterations are being discovered, the sites will need guidance on the eligibility of their participants. Due to data privacy laws, participants will need to sign a prescreening consent form for Incyte to be able to review the genomic alterations of these participants.

## 17. Section 8.1.2, Prescreening and Screening Procedures

**Description of change:** Revised the statement regarding the review of results from the screening visit evaluations to confirm eligibility to indicate that the results will be reviewed by the investigator.

**Rationale for change:** Clarification that no reviews are performed by Incyte or the contract research organization to confirm eligibility.

## 18. Section 8.1.4, Distribution of Reminder Cards

**Description of change:** Removed text explaining that the reminder card will include an area regarding the contents of the participant's last meal.

**Rationale for change:** Administrative error.

## 19. Section 8.3.1, Adverse Events

**Description of change:** Added text to indicate that, for Japanese participants, the relationship with phosphate binders should also be collected on the Adverse Events Form in the eCRF.

**Rationale for change:** Requirement for Japan.

## 20. Section 8.3.6, Laboratory Assessments

**Description of change:** Clarified that serum phosphate testing will be required on Day 8 in Cycles 2+, rather than just on a more frequent basis, if a participant develops hyperphosphatemia during Cycle 1.

**Rationale for change:** To align with Table 4.

## 21. Section 8.3.6, Laboratory Assessments (Table 14: Required Laboratory Analytes)

**Description of change:** Added text that bicarbonate or CO2 is not applicable for Japan.

**Rationale for change:** This is not a standard test in Japan.

## 22. Section 8.5.1, Tumor for Genomics Testing for FGFR Genetic Alterations and Gene Expression

**Description of change:** Added text that if a screening sample has already been analyzed by Foundation Medicine, Inc, as the local laboratory, then the site does not need to send another sample to Foundation Medicine, Inc, for central confirmation.

**Rationale for change:** The original wording did not explain that participants who use the central genomics laboratory, Foundation Medicine, Inc, as their local laboratory will not need to have their tissue- or plasma-based molecular assays retested to document an activating FGFR1, FGFR2, or FGFR3 mutation or gene rearrangement.

## 23. Section 9.2, Definition of Serious Adverse Event

**Description of change:** Added text about an event leading to disability for Japan.

**Rationale for change:** Requirement for Japan.

## 24. Section 9.4, Reporting of Serious Adverse Events

**Description of change:** Added text to indicate that SAEs must be reported to the head of the study site, suspected expected deaths and life-threatening events will be reported to the PMDA, and events related to phosphate binder use for the treatment of hyperphosphatemia will be reported as SAEs in Japan.

**Rationale for change:** Requirement for Japan.

## 25. Section 9.7, Product Complaints

**Description of change:** Added text for unapproved medical devices in Japan.

**Rationale for change:** Requirement for Japan.

## 26. Section 10.2, Populations for Analysis (Table 16: Populations for Analysis); Section 10.5, Interim Analysis

**Description of change:** Clarified the RECIST/RANO evaluable populations.

**Rationale for change:** Clarification requested by internal team.

## 27. Section 10.5, Interim Analysis

**Description of change:** Clarified that patients who are discontinued from treatment without post-treatment tumor assessments will be included in the interim analysis.

**Rationale for change:** Clarification requested by internal team.

## 28. Section 11.1, Investigator Responsibilities

**Description of change:** Added record retention requirements for Japan.

**Rationale for change:** Requirement for Japan.

## 29. Section 11.6, Study and Site Closure

**Description of change:** Added text to reflect the responsibility of the investigator and head of study site (Japan) upon study completion.

**Rationale for change:** Requirement for Japan.

## 30. Appendix A, Information Regarding Effectiveness of Contraceptive Methods

**Description of change:** Clarified which forms of contraception are not applicable in Japan.

**Rationale for change:** Requirement for Japan.

## 31. Appendix E, COVID-19 Pandemic Mitigation Strategies and Instructions

**Description of change:** Added Appendix E.

**Rationale for change:** To provide sites with Protocol-related guidance in response to the COVID-19 pandemic.

## 32. Incorporation of administrative changes.

Other minor, administrative changes have been incorporated throughout the Protocol and are noted in the redline version of the amendment.

## Amendment 2 (14 JAN 2020)

**Overall Rationale for the Amendment:** To incorporate updates of the cohort definitions and other changes based on FDA review of other pemigatinib protocols.

1. **Section 1, Protocol Summary (Figure 1, Study Design Schema); Section 2.1.2, Solid Tumor Malignancies With Activating FGFR Mutations and Translocations; Section 3, Objectives and Endpoints; Section 4, Overall Design; Section 5.1, Inclusion Criteria; Section 8.5.1, Tumor for Genomics Testing for FGFR Genetic Alterations and Gene Expression; [REDACTED]**  
**Appendix C, Activating FGFR Mutations and Translocations**

**Description of change:** [REDACTED]

[REDACTED] added the coordinating principal investigator; refined the definitions of the cohorts; and added language for capping of cohorts.

**Rationale for change:** To provide more clarity regarding analysis of efficacy data and to ensure proper enrollment of participants into the correct cohort.

2. **Section 1, Protocol Summary (Table 3: Schedule of Activities); Section 8.3.5, Comprehensive Eye Examination**

**Description of change:** Added mandatory OCT testing at baseline and every 3 cycles as part of normal eye exams.

**Rationale for change:** Per FDA requirement.

3. **Section 1, Protocol Summary (Table 4: Schedule of Laboratory Assessments); Section 8.3.6, Laboratory Assessments**

**Description of change:** Removal of reference to central laboratory testing for safety laboratory assessments. Added qualifications/windows around requirement for testing.

**Rationale for change:** All safety laboratory testing will be performed locally and testing windows were added to decrease blood draws, if applicable.

5. **Section 6.5.1, Criteria and Procedures for Dose Interruptions and Adjustments of Study Drug; Section 6.5.3, Up-Titration**

**Description of change:** Updated the language to allow up-titrated participants to reduce dose down to 4.5 mg (3 dose reductions).

**Rationale for change:** To allow equal dose reduction limits to all participants.

6. **Incorporation of administrative changes.** Other minor, administrative changes have been incorporated throughout the Protocol and are noted in the redline version of the amendment.

## **Amendment 1 (14 FEB 2019)**

**Overall Rationale for the Amendment:** To incorporate updates based on VHP review of other pemigatinib protocols and to update safety information based on the revised/updated IB.

### **1. Section 1, Protocol Summary; Section 4.1, Overall Design; Section 5.1, Inclusion Criteria (Criterion 4); Appendix C, FGFR Mutations and Translocations**

**Description of change:** Updated the description of Cohort A to include FGFR2 intron 17 rearrangements. Updated the description of Cohort C to include FGFR1/FGFR3 rearrangements with unknown partners.

**Rationale for change:** To clarify cohort assignment for participants with unknown fusion partners.

### **2. Section 1, Protocol Summary (Table 4, Schedule of Laboratory Assessments); Section 8.3.6, Laboratory Assessments**

**Description of change:** Included additional testing of parathyroid hormone every 3 cycles starting with Cycle 3.

**Rationale for change:** VHP request.

### **3. Section 1, Protocol Summary (Table 4, Schedule of Laboratory Assessments)**

**Description of change:** Added coagulation assessments on Day 1 of each cycle.

**Rationale for change:** Table was updated to reflex the coagulation test in the Protocol text.

### **4. Section 2.2.2, Justification for Dose and Regimen**

**Description of change:** Added language to support the prohibition of potent CYP3A4 inhibitors and inducers and moderate inducers.

**Rationale for change:** VHP request.

### **5. Section 2.3, Benefit/Risk of Pemigatinib**

**Description of change:** Updated clinical safety experience with data from the current IB (Edition 5 dated 14 JAN 2019).

**Rationale for change:** To align the Protocol with the updated IB.

### **6. Section 5.2, Exclusion Criteria**

**Description of change:** Criterion 1 updated to exclude participants who have received a prior FGFR inhibitor. The time frame of "within the past 6 months" has been removed.

**Rationale for change:** Participants cannot have received a prior FGFR inhibitor.

### **7. Section 5.2, Exclusion Criteria**

**Description of changes:** In exclusion criterion 9 (Table 9, Exclusionary Laboratory Values), modified the exclusion criteria for liver function tests. Added new criterion 26

to exclude participants with a history of hypovitaminosis D requiring supraphysiologic doses to replenish the deficiency.

**Rationale for changes:** VHP request.

8. **Section 6.5.1, Criteria and Procedures for Dose Interruptions and Adjustments of Study Drug (Table 10, Guidelines for Interruption and Restarting of Study Drug); Section 6.5.4, Criteria for Permanent Discontinuation of Study Drug**

**Description of change:** Added language to discontinue study drug if extreme changes in ECG output occur.

**Rationale for change:** VHP request.

9. **Section 6.5.1, Criteria and Procedures for Dose Interruptions and Adjustments of Study Drug; Section 6.5.3, Up-Titration**

**Description of change:** Added guidance on recommended maximum 2 dose level reductions for participants who are up-titrated to pemigatinib 18 mg.

**Rationale for change:** To provide additional guidance on allowed dose reductions.

10. **Section 6.5.2, Management of Hyperphosphatemia**

**Description of change:** Added examples of diet controls and phosphate binders to treat hyperphosphatemia.

**Rationale for change:** VHP request.

11. **Section 6.6, Concomitant Medications, Appendix D, CYP3A Inhibitors and Inducers**

**Description of change:** Added language to support the prohibition of potent CYP3A4 inhibitors and inducers and moderate inducers. A list of CYP3A4 inhibitors and inducers was added in Appendix D.

**Rationale for change:** VHP request.

12. **Incorporation of administrative changes.** Other minor, administrative changes have been incorporated throughout the Protocol and are noted in the redline version of the amendment.

Signature Page for VV-CLIN-000652 v4.0

Approval	[REDACTED]
	Approver
	16-Feb-2021 07:53:13 GMT+0000

Approval	[REDACTED]
	Document Preparer
	16-Feb-2021 08:12:58 GMT+0000

Approval	[REDACTED]
	Approver
	16-Feb-2021 12:25:39 GMT+0000

Approval	[REDACTED]
	Approver
	16-Feb-2021 20:41:39 GMT+0000

Signature Page for VV-CLIN-000652 v4.0

SD	stable disease
SAP	Statistical Analysis Plan
SOC	system organ class
TEAE	treatment-emergent adverse event
WHO	World Health Organization

1. INTRODUCTION

This is a Phase 2, open-label, single-arm, multicenter study in participants with previously treated locally advanced/metastatic or surgically unresectable solid tumor malignancies harboring activating FGFR mutations or translocations. Section 2 of the Protocol provides a detailed description of the investigational product, target patient population, rationale for doses to be examined, and potential risks and benefits of treatment with pemigatinib.

The purpose of this SAP is to provide details of the statistical analyses that have been outlined in the Study INCB 54828-207 Protocol.

2. STUDY INFORMATION, OBJECTIVES, AND ENDPOINTS

2.1. Protocol and Case Report Form Version

This SAP is based on INCB 54828-207 Protocol Amendment 2 dated 14 JAN 2020 and CRFs approved on 12 APR 2020. Unless superseded by an amendment, this SAP will be effective for all subsequent Protocol amendments and eCRF versions.

2.2. Study Objectives and Endpoints

[Table 1](#) presents the objectives and endpoints.

Table 1: Objectives and Endpoints

Objectives	Endpoints
Primary	

• To evaluate the efficacy of pemigatinib in participants with locally advanced/metastatic or surgically unresectable solid tumor malignancy with an activating FGFR mutation or translocation.	
• ORR in Cohort A, defined as the proportion of participants in Cohort A who achieve a CR or PR based on RECIST v1.1 or RANO.• ORR in Cohort B, defined as the proportion of participants in Cohort B who achieve a CR or PR based on RECIST v1.1 or RANO.• An independent radiological review committee will determine response.

Table 1: Objectives and Endpoints (Continued)

Objectives	Endpoints
Secondary	

• To evaluate other clinical efficacy measurements of pemigatinib in participants with locally advanced/metastatic or surgically unresectable solid tumor malignancy with an activating FGFR mutation and/or translocation.• Safety and tolerability of pemigatinib.	
• PFS, defined as the time from first dose until PD (according to RECIST v1.1 or RANO and assessed by an ICR) or death (whichever is first) in Cohorts A and B, respectively.• DOR, defined as the time from the date of first assessment of CR or PR until the date of the first PD by an ICR per RECIST v1.1 or RANO, or death (whichever is first) in Cohorts A and B, respectively.• OS, defined as the time from first dose of study drug to death of any cause in Cohorts A and B, respectively.• Safety and tolerability, as assessed by the occurrence of TEAEs and treatment-related AEs according to NCI CTCAE v5.0, physical exam changes, vital sign changes, laboratory evaluations, and ECGs in each cohort.

3. STUDY DESIGN

This is an open-label, monotherapy study of pemigatinib in participants with advanced/metastatic or surgically unresectable solid tumor malignancy harboring an activating FGFR mutation or translocation. This study consists of 3 cohorts, Cohort A, Cohort B, and Cohort C and will enroll approximately 60 participants, 90 participants, and 20 participants, respectively (see [Figure 1](#)).

Participants will receive a QD dose of pemigatinib at 13.5 mg continuously as long as participants are receiving benefit and have not met any criteria for study withdrawal.

Participants with local laboratory test results (eg, tissue or plasma-based molecular assays) documenting an activating FGFR1, FGFR2, or FGFR3 mutation or gene rearrangement are eligible to enroll as long as the results meet the cohort criteria. Confirmatory testing through the central genomics laboratory will be performed for all participants; however, results from the central genomics laboratory are not required before enrollment. Centralized genomic testing results will allow participants to be assigned to a cohort:

[figure not shown]
- Cohort A: FGFR1-3 in-frame fusions or FGFR2 rearrangements* (n = 60)
- Cohort B: Known or likely activating mutations (excluding kinase domain) in FGFR1-3 included in Appendix C of Protocol Amendment 2 dated 14 JAN 2020 (n = 90)
- Cohort C: Known activating mutations in the kinase domain of FGFR1-3, other likely activating FGFR1-3 mutations or FGFR1/FGFR3 rearrangements* (requires consultation with the sponsor) (n = 20)

*Only FGFR fusions or rearrangements with an intact kinase domain are eligible.

Please note that there is no difference in the treatment regimen between the cohorts. The sponsor may choose to cap enrollment of any one tumor type and/or FGFR alteration to allow representation of multiple tumor types and avoid analysis being influenced by any one tumor type. The sponsor may also choose to cap enrollment of any one tumor type if no benefit is being seen in previous participants enrolled.

[figure not shown]
For participants with FGFR2-rearranged cholangiocarcinoma, enrollment is limited to no more than 10 participants into Cohort A; for participants with FGFR3 mutation or fusions bladder cancer, enrollment is limited to no more than 10 participants into Cohort A or B combined. Participants from either group noted must have mandatory baseline and at least 1 on-treatment biopsy.

PPD

A fresh biopsy at baseline (or archival tissue that was collected less than 12 months from date of screening) and at least 1 on-treatment biopsy is required for participants with safely accessible lesions. Treatment will start on Day 1. Participants will undergo regular safety assessments during treatment as well as regular efficacy assessments. Participants will be allowed to continue administration in 21-day cycles until documented disease progression or unacceptable toxicity is reported.

Figure 1: Study Design Schema

*Only FGFR fusions or rearrangements with an intact kinase domain are eligible.

CR = complete response; D/C = discontinue; FGF = fibroblast growth factor; FGFR = fibroblast growth factor receptor; PD = progressive disease; PR = partial response; SD = stable disease; SF = screen failure; tx = treatment.

3.1. Randomization

Not applicable.

3.2. Control of Type I Error

For the primary endpoint, the overall 1-sided Type I error is 0.025. The primary endpoint in Cohort A and Cohort B will be tested sequentially at 1-sided 0.025. If ORR in Cohort A is significant, then ORR in Cohort B will be tested.

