### **10.3. Level of Significance**

The overall level of significance is 1-sided 0.025. The primary endpoint in Cohort A and Cohort B will be tested sequentially at 1-sided 0.025. If ORR in Cohort A is significant, then ORR in Cohort B will be tested.

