3.3. Sample Size Considerations

For Cohort A, approximately 60 participants are planned. Assuming the true ORR is 35% for the intervention in this group, 60 participants are needed to ensure that there is at least 90% power to reject the null hypothesis of $ORR \leq 15\%$. This calculation assumes 1-sided test at the overall 0.025 level of significance.

For Cohort B, approximately 90 participants are planned. Assuming the true ORR is 30% for the intervention in this group, 90 participants are needed to ensure that there is at least 90% power to reject the null hypothesis of $ORR \leq 15\%$. This calculation assumes 1-sided test at the overall 0.025 level of significance.

For Cohort C, approximately 20 participants will be enrolled, which will provide at least 80% chance of observing at least 4 responders in this cohort if the underlying ORR is 30%.

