7.1. Efficacy Hypotheses

Objective Response Rate (Primary Endpoint): Administration of pemigatinib to participants in Cohort A and B improves ORR from 15%. Assume ORR_A and ORR_B are the ORRs for cohort A and B respectively.

The hypotheses for Cohort A are as follows:

- H_0 (null hypothesis): $ORR_A \leq 15\%$
- H_A (alternative hypothesis): $ORR_A > 15\%$

The hypotheses for cohort B are as follows:

- H_0 (null hypothesis): $ORR_B \leq 15\%$
- H_A (alternative hypothesis): $ORR_B > 15\%$

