7.2. Analysis of the Primary Efficacy Parameter

7.2.1. Primary Efficacy Analysis

The primary endpoints of the study are ORR in Cohort A and Cohort B, respectively. Objective response rate is defined as the proportion of participants who achieved a CR or a PR based on RECIST v1.1 or RANO, as assessed by an independent centralized radiological review committee. Confirmation of CR and PR is required and documented in the Independent Central Review Charter. This analysis will be based on the efficacy evaluable population. Participants

who do not have sufficient baseline or on-study response assessment information to be adequately assessed for response status will be included in the denominators in the calculation of ORR. The 95% CI for the ORR will be estimated using the Clopper-Pearson method. The p-value from the exact binomial test will be provided.

The ORR will also be analyzed based on the PP population as a sensitivity analysis.

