9. INTERIM ANALYSIS

For Cohort A, futility analysis will be performed when approximately 25 participants are enrolled into the cohort and have at least 2 objective tumor response assessments per independent centralized radiological review or are discontinued from the study. Cohort A can be stopped for futility if ≤ 4 responders are observed, for which there is $< 10\%$ probability of claiming ORR $> 15\%$ at final analysis. This rule is just a guidance and nonbinding.

For Cohort B, futility analysis will be performed when approximately 35 participants are enrolled into the cohort and have at least 2 objective tumor response assessments per independent centralized radiological review or are discontinued from the study. Cohort B can be stopped for futility if ≤ 6 responders are observed, for which there is approximately 14% probability of claiming ORR $> 15\%$ at final analysis. This rule is just a guidance and nonbinding.

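### The A-then-B sequence is valid but leaves 0.0114 of the 0.025 unused at the planned Cohort A size, so Cohort B forgoes an error-controlled test it could have when A fails

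*SAP*

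**What the plan says.** SAP 3.2 sets the error budget: "For the primary endpoint, the overall 1-sided Type I error is 0.025". Protocol 10.3 gives the order: "The primary endpoint in Cohort A and Cohort B will be tested sequentially at 1-sided 0.025". Both documents then gate Cohort B on Cohort A: "If ORR in Cohort A is significant, then ORR in Cohort B will be tested".

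The null response rate is 15% in each cohort (SAP 7.1). The test is exact: "The p-value from the exact binomial test will be provided" (SAP 7.2.1), alongside a 95% Clopper-Pearson interval. SAP 3.3 plans about 60 participants in A (true rate 35%) and about 90 in B (true rate 30%), each with at least 90% power at 1-sided 0.025.

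Cohort A also has a nonbinding look at about 25 participants. Under SAP 9, "Cohort A can be stopped for futility" if 4 or fewer responders are seen. B has a similar look at about 35, with a limit of 6.

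Neither document gives critical response counts, the attained size of either test, or any use of unspent error. Neither says what becomes of B's formal test if A is stopped.

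**The concern.** The response rates in A and B are both primary endpoints, and B is the larger cohort, with a different class of alteration. Under the gate, B's formal conclusion depends on A's result. If A falls short, B has no error-controlled test however well it performs.

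That loss would be the price of error control if A used the whole 0.025. An exact test on 60 participants cannot do so, because responder counts come in whole numbers. The question is whether the unused part can support a worthwhile test of B.

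**Working it through.** **Inputs.** Null 15%, 1-sided 0.025, exact binomial (SAP 3.2, 7.1, 7.2.1). Planned sizes 60 and 90; design rates 35% and 30% (SAP 3.3). Looks: A stops at ≤4/25, B at ≤6/35 (SAP 9). Below, T(n, r, p) = P(X ≥ r) for X ~ Bin(n, p).

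**1. The plan's own power.**
- A: T(60, 15, 0.15) = 0.0291 exceeds 0.025 and T(60, 16, 0.15) = 0.0136 does not, so A needs 16. Power T(60, 16, 0.35) = 93.4%.
- B: T(90, 20, 0.15) = 0.0434 and T(90, 21, 0.15) = 0.0240, so B needs 21. Power T(90, 21, 0.30) = 93.5%.

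Both meet the stated 90%.

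**2. What is left over.** 0.0250 − 0.0136 = 0.0114.

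**3. The test of B that fits.** T(90, 22, 0.15) = 0.0126 is too large; T(90, 23, 0.15) = 0.0062 fits. Power T(90, 23, 0.30) = 85.0%.

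**4. Familywise error with this fallback test added.**
- Both nulls true: 0.0136 + (1 − 0.0136) × 0.0062 = 0.0198. The plain sum, which needs no independence, is also 0.0198.
- Only B's null true: at most 0.0240, the larger of B's two test sizes.
- Only A's null true: 0.0136.

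**5. B's chance of formal success at a true rate of 30%, no futility stops.** With a = P(A significant), the plan gives a × 0.9355 and the fallback adds (1 − a) × 0.8500.

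| True rate in A | a | Plan | With fallback |
|---|---|---|---|
| 35% (design) | 0.9344 | 87.4% | 93.0% |
| 30% | 0.7562 | 70.7% | 91.5% |
| 25% | 0.4312 | 40.3% | 88.7% |

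**6. The same with both futility rules followed.** A's success probability is the sum over x = 5 to 25 of P(x of 25) × T(35, 16 − x, p), which is 0.9169 at 35% and 0.4086 at 25%. The matching sum for B (7 or more of 35, then 55 more participants) is 0.8932 for a threshold of 21 and 0.8223 for 23.
- A at 35%: 0.9169 × 0.8932 = 81.9%; adding 0.0831 × 0.8223 gives 88.7%.
- A at 25%: 0.4086 × 0.8932 = 36.5%; adding 0.5914 × 0.8223 gives 85.1%.

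**7. Dependence on A's final size.** The planned 60 is approximate.

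| Final n in A | A's size | Left over | B needs (of 90) | Power at 30% |
|---|---|---|---|---|
| 58 | 0.0218 | 0.0032 | 24 | 78.8% |
| 59 | 0.0115 | 0.0135 | 22 | 89.9% |
| 60 | 0.0136 | 0.0114 | 23 | 85.0% |
| 62 | 0.0186 | 0.0064 | 23 | 85.0% |
| 63 | 0.0215 | 0.0035 | 24 | 78.8% |
| 64 | 0.0248 | 0.0002 | 28 | 44.8% |

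Over n = 54 to 66, power is at least 85.0% at 10 of the 13 sizes.

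**8. Why the size must be used consistently.** Suppose the n = 60 leftover is used after an early stop, but A would otherwise have run to 64. With both nulls true and the futility rule followed, A rejects with probability 0.0218 and stops early with probability 0.682. The error is about 0.0218 + 0.682 × 0.0062 = 0.026, above 0.025.

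**The case against.** The strongest reply is that nothing here is wrong. A fixed sequence is a standard procedure, it was prespecified, and it puts the cohort with the larger assumed effect first. That stands. A reader might infer that the plan inflates error or overstates its power. The documents support neither: error is at most 0.025, and the 90% is stated per cohort and met.

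A reader might also infer that B's result would be lost. It would not. B's response rate, interval and p-value are planned whatever A shows (SAP 7.2.1). Only the multiplicity-controlled claim is lost, which matters less in a single-arm Phase 2 trial than in a confirmatory one.

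Three further points stand in part:
- The larger gains need A's true rate to be well below the planned 35%. At the design rates the gain is 93.0 − 87.4 = 5.6 points.
- The leftover varies with A's final size, which is not fully controlled because central genomics assigns the cohort and its result is not required before enrolment (Protocol 4.1). This limits the gain but rarely removes it. Even at 64 the added test is a real one, at 28 of 90.
- The study is open-label, and both looks use response data. A change made after those data are seen would look data-driven even if the error bound held on paper.

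**Conclusion.** This is an available efficiency gain, not a defect. At 60 and 90 participants, adding the fallback keeps every result that would be significant under the plan and adds a test of B where there is none now. Familywise error stays at or below 0.0240.

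At the design rates, B's chance of formal success rises by 5.6 points without futility stops (87.4% to 93.0%) and by 6.8 points with both rules followed (81.9% to 88.7%). With A at 25% the rise is about 48 points either way.

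These figures assume exact tests, independent cohorts, a true rate of 30% in B, and final sizes of 60 and 90. The error bound with both nulls true does not need independence. That an early stop of A would remove B's formal test is an inference from the gate; the documents do not say so.

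**What to change.** In SAP 3.2 and Protocol 10.3:

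1. Test A as now.
2. If A is significant, test B at 1-sided 0.025 as now (21 of 90).
3. If A is not significant, test B at 0.025 minus the attained size of A's exact test. At 60 participants this is 0.0114, or at least 23 of 90.
4. State which size of A is used. The n = 60 leftover may be applied after an early stop only if A's analysis size is fixed at 60 in advance. Otherwise, after a stop, use the smallest leftover over a stated permitted range. A range of 59 to 62, for example, has a smallest leftover of 0.0064 and still allows 23 of 90; a range that includes 64 pushes the threshold to 28.
5. Give the critical counts for both cohorts, and say explicitly that step 3 applies when A stops for futility.

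Fix the rule before any response data are reviewed, including at the futility looks; database lock is too late in an open-label study. Protocol 2.3 shows that this study was already under way at the November 2020 safety cutoff, so the sponsor should document what response data had been reviewed when the change was made.

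The cost is one paragraph in each document and a stricter threshold for B when A fails (23 rather than 21 of 90), where there is now no test. No participants are added and A's threshold does not change.
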